## 5 STUDY ENROLLMENT AND WITHDRAWAL

To achieve 420 evaluable subjects, approximately 560 adults aged 18 years or older who meet all inclusion criteria and no exclusion criteria will be enrolled. No exemptions are granted on inclusion/exclusion criteria in trials sponsored by the Division of Microbiology and Infectious Diseases (DMID). Subjects may be recruited from STI clinics, HIV clinics, student health centers, and the public via advertising (e.g., flyers, radio, newspaper, social media). To enhance recruitment and retention, sites may seek institutional review board (IRB) permission to contact subjects by phone, text messaging, and/or email as appropriate. Any communication with subjects must be made using devices, methods, and services allowed by the local IRB and must be documented appropriately. As noted in Section 7.1, each subject may indicate his/her preferred method of contact to the study staff.

### 5.1 Subject Inclusion Criteria

Subjects eligible to enroll in this study must meet all inclusion criteria:

1. Subject is aged 18 years or older.
2. Subject has provided informed consent.
3. Subject has untreated primary\*, secondary\*\*, or early latent\*\*\* syphilis.
  - \*Primary syphilis is characterized by the presence of an ulcerative lesion at a potential site of inoculation (while classically solitary, shallow, painless and with an indurated, clean base, primary lesions may be multiple, may vary considerably in appearance, and/or may not be painless) or by darkfield, acceptable polymerase chain reaction (PCR), or direct fluorescence antibody-*T. pallidum* (DFA-TP) positive ulcers.
  - \*\*Secondary syphilis is characterized by classical palmar/plantar rash, condylomata lata, mucous patches, etc. or by darkfield, acceptable PCR, or DFA-TP positive lesions.
  - \*\*\*Early latent syphilis is characterized by current reactive serologic tests for syphilis (STS) and a documented non-reactive STS, or documented sexual exposure to an individual known to have primary, secondary, or early latent syphilis diagnosed within the last 12 months.
4. Subject either has a newly reactive non-treponemal test (such as an RPR test) or a history of syphilis and a current increase in RPR titer of two or more dilutions (i.e., four-fold).
5. If subject is of childbearing potential, subject has a negative urine or serum pregnancy test.
6. Subject is willing to have an HIV test, participate in HIV counseling, and return to clinic for follow-up.
7. In the opinion of the investigator, subject is able and willing to comply with study procedures, including receipt of three BPG injected doses if randomized to Arm 2.

8. If female, subject must be of non-childbearing potential\* or must be using an acceptable method of birth control\*\* to avoid becoming pregnant.

\*Non-childbearing potential is defined as being post-menopausal for at least 1 year, status after bilateral tubal ligation, or status after bilateral oophorectomy, or status after hysterectomy.

\*\*Subject must agree to avoid becoming pregnant by using one of the following acceptable methods of birth control for the entire duration of participation in the trial:

- Intrauterine contraceptive device; OR
- Oral contraceptives; OR
- Hormonal injections; OR
- Hormonal implants; OR
- Contraceptive patches; OR
- Monogamous relationship with vasectomized partner; OR
- Exclusively same-sex relationships; OR
- Use of condoms by the male partner; OR
- Abstinence

## 5.2 Subject Exclusion Criteria

Subjects eligible to enroll in this study must not meet any exclusion criteria:

1. Subject previously enrolled in this trial.
2. Subject has latent syphilis of unknown duration, late latent syphilis, or evidence of neurosyphilis, including ocular syphilis.\*  
\*e.g., eye pain/redness, recent ocular change, and/or changes in visual acuity
3. Subject has a known or suspected allergy or hypersensitivity to penicillin or other beta-lactam antibiotics.
4. Subject has a known or suspected STI other than syphilis requiring treatment with a drug active against *T. pallidum*.
5. Subject has used antibiotics\* active against *T. pallidum* in the preceding 30 days.  
\*Note: the use of antimicrobials known to NOT be effective against *T. pallidum* (e.g., quinolones, sulfonamides, trimethoprim, metronidazole, spectinomycin) will be allowed.
6. Subject has suspected or known ongoing drug use that might interfere with study participation and follow-up treatment.
7. Subject is breastfeeding.
8. Subject has used an investigational drug in the past 30 days that might interfere with safety or efficacy assessment.\*  
\*If the subject has used any investigational drugs in the past 30 days, contact the Principal Investigator, DMID Clinical Project Manager, DMID Medical Officer, and FHI 360 to confirm eligibility.
9. Subject has any other condition that, in the opinion of the investigator, would interfere with participation in the study.

---

## 5.3 Treatment Assignment Procedures

### 5.3.1 Randomization Procedures

Enrollment of subjects will be done online using the enrollment module of Emmes Advantage eClinical®. Subjects will be randomized at a 1:1 ratio to receive one of the two BPG treatments after informed consent is obtained and their eligibility is confirmed.

The study will use a stratified, permuted block-randomization scheme. Permuted block randomization is used to avoid the potential for serious imbalance in the number of subjects assigned to each group, an imbalance that can occur in the simple randomization procedures. Stratification will be by study site. While HIV status may not be known at the time of randomization, subjects will be classified as HIV-infected or HIV-uninfected to assess the secondary HIV status subgroup objective, and randomization will be limited as follows:

- If 280 subjects who were HIV-infected at baseline are confirmed evaluable, additional subjects who are known to be HIV-infected will not be allowed to enroll thereafter, while HIV-uninfected subjects and subjects of unknown HIV status may continue to enroll.
- If 140 subjects who were HIV-uninfected at baseline are confirmed evaluable, only subjects who are known to be HIV-infected will be allowed to enroll thereafter.

The list of randomized treatment assignments will be prepared by statisticians at Emmes and included in the enrollment module of its Internet Data Entry System (IDES). IDES will assign each subject a treatment code from the list after demographic and eligibility data have been entered.

Instructions for use of the enrollment module are included in the IDES User's Guide. Manual back-up randomization procedures are provided in the Manual of Procedures (MOP) for use in case a site temporarily loses access to the Internet or the online enrollment system is unavailable.

### 5.3.2 Masking Procedures

Neither subjects nor providers will be masked in this study. The outcome (serological response to therapy) is objective—furthermore, laboratory staff will be blinded to subject ID and treatment assignment—and it would not be ethical to give subjects placebo injections.

### 5.3.3 Reasons for Withdrawal from Study Participation/Discontinuation of Study Treatment

Subjects may voluntarily withdraw their consent for further study participation or may request to discontinue study treatment at any time and for any reason without penalty or prejudice to future

medical care.

In addition to voluntarily requesting to discontinue study treatment as noted above, subjects randomized to Arm 2 may also be discontinued from additional treatment after discussion with the investigator for the following reasons:

- AE(s) judged to be Grade 3 and related to study drug
- SAE(s) judged to be related to study drug
- Investigator's discretion
- Violation of eligibility criteria
- Significant deviation from the treatment plan specified in the protocol (e.g., incorrect administration of BPG, failure to attend study visits)
- Receipt of antibiotic therapy active against *T. pallidum* for treatment of syphilis infection

Subjects in either arm who require off-study retreatment for syphilis infection will be withdrawn from the study after completing an Early Termination Visit.

#### **5.3.4 Handling of Withdrawals from Study Participation/Discontinuations of Study Treatment**

Subjects who withdraw from study participation, or are excluded from any efficacy endpoint analysis, or are lost to follow-up after signing the informed consent form (ICF), randomization, and receipt of the first dose of BPG will not be replaced. Subjects who withdraw consent after signing the ICF and randomization but before receipt of the first dose of BPG may be replaced.

If the subject requests to discontinue study treatment at any time after the first dose of BPG, the subject will be asked to continue scheduled study procedures including safety and efficacy evaluations, if possible, and be given appropriate care under medical supervision if symptoms of any AE related to participation in the study are continuing. The subject will be followed until the AE is resolved or until the subject's condition becomes stable.

Subjects who request to discontinue study treatment at any time after the first dose of BPG will be reminded of the importance of continuing in the study for safety evaluations. Subjects will be encouraged to complete the Early Termination Visit if they choose not to complete the remaining study visits (i.e., if they withdraw from study participation). The Early Termination Visit procedures are listed in Section 7.3. Subjects who choose to withdraw from study participation will no longer be contacted for follow-up.

In the case of subjects who fail to appear for a follow-up safety assessment, extensive effort (e.g., three documented contact attempts via phone calls, e-mails, etc., made on separate occasions and followed by a certified letter) will be made to locate or recall them, or at least to determine their health status. Subjects who cannot be located after extensive effort will no longer be contacted for follow-up. These efforts will be documented in the subject's records.

If a subject is withdrawn from the study due to an AE that prohibits continued participation in the study, s/he will be given appropriate care and treatment under medical supervision until the condition has resolved or becomes stable.

Safety and efficacy data will be collected on any subject who is excluded from any efficacy endpoint analysis. Refer to Section 11 for details on how subjects who are withdrawn will be handled during analysis.

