## 4 STUDY DESIGN

This is a Phase 4, open-label, multicenter trial to evaluate the efficacy of a single injected dose of BPG 2.4 MU (Arm 1) compared to three successive weekly injected doses of BPG 2.4 MU (Arm 2) for treatment of early syphilis in HIV-infected and HIV-uninfected subjects. Subjects will be aged 18 years or older with untreated early syphilis (primary, secondary, or early latent as defined in prior syphilis treatment trials of the Sexually Transmitted Infections Clinical Trials Group (STI CTG)). The study will be conducted at 10 sites in the US and will enroll approximately 560 subjects to achieve 420 evaluable.

The study will involve a screening/enrollment visit and seven scheduled follow-up visits (Weeks 1 and 2, and Months 1, 3, 6, 9, and 12) over a 12-month period. At the enrollment visit, after providing informed consent, all subjects will undergo a brief sexual and medical history and a directed physical examination; all women of childbearing potential will have a urine or serum pregnancy test performed as part of qualification for study participation; all subjects will undergo phlebotomy for serological testing for syphilis and HIV according to the study and clinic protocols. All subjects who have not been tested for chlamydia and gonorrhea since last sexual activity and all subjects who have been sexually active in the past 14 days will have specimens collected for chlamydia and gonorrhea testing. Subjects will have specimens collected for other STI testing as indicated by local standard of care and subject history. All eligible subjects will be randomized to Arm 1 or Arm 2 and will receive an injected dose of BPG 2.4 MU.

Study personnel will attempt to contact subjects approximately 24 hours after Visit 1 to assess for symptoms of a Jarisch-Herxheimer reaction as described in Section 8.1. At the second and third visits (Weeks 1 and 2 of follow-up), subjects randomized to Arm 2 will receive injected doses of BPG 2.4 MU.

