### 7.1 Visit 1 – Screening and Enrollment/Baseline Visit (Day 1)

- The potential subject will be provided with a description of the study (purpose and study procedures) and asked to read the ICF or have it read to him/her. The ICF must be signed before any screening or study procedures are performed.
- Demographic information will be collected from the subject.
- Eligibility criteria will be reviewed with the subject.
  - Complete medical history will be obtained by interviewing subjects (and reviewing medical records for the past 14 days, if available) to assure eligibility. If available in the medical record, the most recent viral load result from the past six months prior to enrollment should be recorded.
  - Sexual history for the past 60 days will be collected.
  - A targeted physical examination will be performed by a qualified study clinician (including vital signs: temperature, heart rate, respiration rate, and blood pressure; and genital, rectal, oral, skin, and lymph node examinations).
  - Study staff will swab consenting subjects' oral cavities and primary or secondary lesions (if lesions are present per Section 5.1); see Section 8.2.2.
  - A urine or serum pregnancy test will be performed on all subjects of childbearing potential and must be negative prior to randomization.
  - All concomitant medications taken in the last 30 days prior to initiating BPG treatment will be recorded on the appropriate data collection form.
  - Blood will be collected for RPR test, storage, and HIV assays (including a CD4 count for persons with known HIV infection whose medical records do not include a CD4 count in the past 30 days, and an HIV test for persons who do not have a previously documented positive HIV test result). Specimens will be collected at sites of exposure for screening/diagnosis of gonorrhea and chlamydia for all subjects who have not been tested since last sexual activity and for all subjects who have been sexually active in the past 14 days and for other STIs as indicated by local standard of care and subject history. Clinicians will provide pre- and post-test counseling, treatment, and referrals per local standard of care.

At this juncture, if a potential subject is not eligible, the reason for screening failure will be recorded and the subject will not be enrolled.

- 
- Subject will be enrolled in Advantage eClinical® and randomly assigned to Arm 1 or Arm 2.

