  - BPG will be administered, and the subject will be observed per clinic standard operating procedure (SOP).
  - Study personnel will discuss with subjects and assess and record all AEs/SAEs (including solicited reactogenicity AEs and other unsolicited AEs).
  - Protocol requirements will be reviewed with the subject.
  - Contact information will be collected, the subject's preferred method of contact will be noted, and the Week 1 visit will be scheduled.
  - The Jarisch-Herxheimer checklist will be distributed and the instructions reviewed with the subject. The subject will be asked to have the completed checklist available for reference during the non-visit contact approximately 24-48 hours after Visit 1 and to bring it to Visit 2. Study personnel will instruct the subject to use a thermometer to take temperature reading(s) at home, if possible, and note the highest temperature if s/he feels feverish any time before being contacted to assess for symptoms of a Jarisch-Herxheimer reaction as described in Section 8.1. Study personnel will attempt to contact subjects by phone call, text message, or email approximately 24 hours after Visit 1 to make this assessment. Note that data will be recorded on the appropriate electronic case report forms (eCRFs) based on subject interview; the Jarisch-Herxheimer checklist completed by the subject will not be retained.

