### 11.4.1 Analysis Populations

Intent-to-Treat (ITT) Population: This analysis population includes all randomized subjects.

Modified Intent-to-Treat (mITT) Population: This analysis population includes all randomized subjects who are eligible at the baseline visit and whose TPPA result is positive at the baseline visit and/or at Visit 5 (Month 3), if repeat testing was performed.

Safety Population: This analysis population includes all randomized subjects who received at least one dose of study treatment.

Evaluable Population: This analysis population includes all randomized subjects who are eligible at the baseline visit, have a known HIV status determined at or before the baseline visit, have positive TPPA results at the baseline visit and/or Visit 5 (Month 3) (if repeat testing was performed), received all assigned doses of BPG, have adequate RPR titer data available at baseline and applicable follow-up visit(s), and (for HIV-uninfected subjects only) HIV-uninfected status persists through applicable follow-up visit(s).

If a subject receives antibiotic(s) active against *T. pallidum* for reasons other than syphilis between enrollment and the applicable follow-up visit(s), the subject will be included in ITT analyses but excluded from Evaluable analyses. If a subject receives antibiotic(s) active against *T. pallidum* between enrollment and the applicable follow-up visit(s) due to local RPR testing results, the subject will be included in all analyses.

A blinded case review committee will review subjects' data to determine if treatment with drug(s) known to be active against *T. pallidum* for reasons other than syphilis infection excludes the subject from the Evaluable analysis population.

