 At Visit 1, record concomitant medications taken in the last 30 days before initiating BPG. At subsequent visits, record all concomitant medications taken since the last visit and update previously recorded medications as appropriate.

 Collect for subjects with known HIV infection whose medical records do not include a CD4 count in the past 30 days; at Visit 4, this is only applicable to subjects newly found to have HIV infection from Visit 1 to Visit 4 (inclusive).

 Perform for subjects who do not have a previously documented positive HIV test result using locally available tests (e.g., nucleic acid tests (NATs), antibody/antigen tests).

 At Visit 1, collect specimens at sites of exposure for screening/diagnosis of chlamydia and gonorrhea for all subjects who have not been tested since last sexual activity and for all subjects who have been sexually active in the past 14 days and for other STIs as indicated by local standard of care and subject history. At subsequent visits, collect specimens at sites of

exposure for STI testing per local standard of care and subject history.

It is optional to swab subject's oral cavity and lesions, if lesions are present. See Section 8.2.2.

 At Visit 1, administer BPG to all subjects. At Visits 2 and 3, administer BPG to subjects in Arm 2 only.

At Visit 1, collect contact information. At subsequent visits, review contact information and update if needed.

 Distribute checklist at Visit 1. Subject refers to completed checklist during Jarisch-Herxheimer assessment; see Sections 7 and 8.1.

Assess per protocol Section 8.1. If subject is not reached, assess at Visit 2.

 Assess and record all AEs/SAEs (including solicited reactogenicity AEs and other unsolicited AEs).

 At Unscheduled Visits, any of the specified evaluations that are relevant to the subject may be performed at the discretion of the site PI.

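### The arm is assigned before a first dose common to both arms, so subjects can leave untreated because of their assignment and still count in the primary ITT comparison

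*Protocol*

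**What the plan says.** Protocol Section 5.3.2 states that "Neither subjects nor providers will be masked in this study". Section 5.3.1 has the enrollment system issue the assignment once demographic and eligibility data are in. Section 7.1 then lists two steps in this order at Visit 1: "Subject will be enrolled in Advantage eClinical ® and randomly assigned to Arm 1 or Arm 2", followed by "BPG will be administered, and the subject will be observed per clinic standard operating procedure (SOP". Section 4 gives the same order.

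The first injection does not depend on the arm. Footnote 10 of Appendix A reads: "At Visit 1, administer BPG to all subjects. At Visits 2 and 3, administer BPG to subjects in Arm 2 only".

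Section 5.3.4 allows for losses between the two steps: "Subjects who withdraw consent after signing the ICF and randomization but before receipt of the first dose of BPG may be replaced". Subjects who leave after the first dose are not replaced.

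Section 11.4.1 defines ITT without any dosing condition: "This analysis population includes all randomized subjects". The Safety population, by contrast, is limited by dosing: "This analysis population includes all randomized subjects who received at least one dose of study treatment". Section 11.4.4.1 makes ITT the primary population. It classes subjects who do not meet the response criteria by Month 6 as non-responders, and it says that ITT subjects without adequate serology will have their response imputed. Last observation carried forward is its only named example, and the details are left to the SAP.

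**The concern.** An unmasked subject can react to the assignment. Because the arm is fixed before an injection that is the same for everyone, that reaction can occur before any treatment is given, and nothing at Visit 1 requires the arm to be known by then.

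A subject who leaves in this gap has a baseline titer, since blood is drawn before randomization, but has no study treatment and no follow-up titer. The subject remains in ITT. The mITT definition has no dosing condition either, so a leaver who is eligible and TPPA-positive at baseline remains there too. A replacement is one more randomized subject; it does not supply the missing outcome.

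If leavers are scored as non-responders, directly or by carrying the baseline titer forward, the arm that loses more has its response rate pulled down. In a noninferiority test, a lower three-dose rate makes the one-dose regimen look better than it is, and a lower one-dose rate makes it look worse.

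**Working it through.** **Inputs.** From Sections 11.1 and 11.2: margin 0.10 (three-dose minus one-dose), one-sided alpha 0.05, Farrington-Manning test, 1:1 allocation, null rates 0.788 (three-dose) and 0.688 (one-dose), alternative rate 0.788 in both arms, 420 evaluable, 560 enrolled. ITT size per arm: 560 / 2 = 280. Assumptions, because the documents give no figure: a share w of one arm leaves before dose 1, w from 0 to 3%, and every leaver is scored as a non-responder.

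**Formula.** With p3 and p1 the response rates as analysed in the three-dose and one-dose arms:

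P(declare noninferiority) = Φ{ [ (0.10 − (p3 − p1))·√n − 1.645·s0 ] / s1 }

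where s1 = √[p3(1−p3) + p1(1−p1)], and s0 is the same expression at the restricted maximum-likelihood rates, which are forced to differ by 0.10.

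**Step 1: reproduce the plan.** n = 210, p3 = p1 = 0.788. The restricted rates are 0.8297 and 0.7297, so s0 = 0.5818 and s1 = 0.5780. Then (0.10 × 14.491 − 1.645 × 0.5818) / 0.5780 = (1.4491 − 0.9571) / 0.5780 = 0.851, and Φ(0.851) = 80.3%, against 80% stated. Enrollment: 420 / 0.75 = 560, as stated. The subgroup powers come out at 72.4% and 38.2%, against 72% and 38% stated.

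**Step 2: leavers in one arm.** The analysed rate in that arm becomes p(1 − w). Three cases at n = 280 (√n = 16.733):

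- *Arm 2 loses 1%, true difference at the margin.* p3 = 0.788 × 0.99 = 0.7801, difference 0.0921, s0 = 0.6212, s1 = 0.6214. (0.1319 − 1.0219) / 0.6214 = −1.432, so the type I error is 0.076.
- *Arm 2 loses 2%, true difference at the margin.* p3 = 0.7722, difference 0.0842, s0 = 0.6245, s1 = 0.6249. (0.2637 − 1.0273) / 0.6249 = −1.222, so the type I error is 0.111.
- *Arm 1 loses 2%, no true difference.* p1 = 0.7722, difference 0.0158, s0 = 0.5877, s1 = 0.5856. (1.4096 − 0.9668) / 0.5856 = 0.756, so the power is 77.5%.

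| w in one arm | Subjects (280w) | Type I error, Arm 2 leaves | Type I error, Arm 1 leaves | Power, Arm 2 leaves | Power, Arm 1 leaves |
|---|---|---|---|---|---|
| 0 | 0 | 0.050 | 0.050 | 89.2% | 89.2% |
| 1% | 2.8 | 0.076 | 0.034 | 92.6% | 84.0% |
| 2% | 5.6 | 0.111 | 0.022 | 95.1% | 77.5% |
| 3% | 8.4 | 0.155 | 0.014 | 96.8% | 69.8% |

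**Step 3: equal leaving.** With the same share in both arms, the type I error is 0.053 at 1% and 0.056 at 2%. The imbalance does the harm, not the leaving as such.

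**Step 4: replacement.** Take 3 leavers from 280 in Arm 2, a share of 3/280 = 1.07%. Even if all three replacements fell in Arm 2, the share would be 3/283 = 1.06%. The leavers are still counted, so replacement hardly changes the result.

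**The case against.** Much of the case on the other side stands.

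- **Nobody is removed from ITT.** A reader might infer from the replacement sentence that pre-dose leavers drop out of the primary analysis. Section 11.4.1 does not support that. The replacement rule causes no ITT bias by itself; any bias comes from how the missing outcome is counted.
- **The direction is not fixed.** A reader might infer that the bias must favour noninferiority, because only Arm 2 faces further injections. Section 2.3.1 lends that some support, naming extra discomfort and bruising. But both arms attend the same Week 1 and Week 2 visits, and Section 2.1 says that many providers already give multiple doses, so some subjects may be disappointed by the single dose. If Arm 1 loses more, the bias runs the other way.
- **The rate is unknown and probably low.** Inclusion criterion 7 requires willingness to take three doses, and assignment and injection fall within one visit.
- **The scoring is partly open.** Imputation is left to the SAP, which is not a fault here. The figures above hold only if leavers end up as non-responders.
- **Disclosure before the injection is inferred** from the order of steps and the lack of masking. No sentence says that the subject is told the arm at that moment, but none withholds it either.
- **The Evaluable analysis excludes undosed leavers.** That is a partial safeguard. It is a secondary analysis, however, and it requires all assigned doses, which is a harder condition in Arm 2.
- **A change of order does not end arm-related dropout.** A subject who disappears just after dose 1 also lacks a follow-up titer and also stays in ITT.

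The last point limits the benefit but does not cancel it. Once dosed, a subject who declines further injections has been treated and, under Section 5.3.4, is asked to continue study evaluations. A subject who withdraws before dose 1 has not been treated at all.

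**Conclusion.** The concern holds in a limited form. The order of steps leaves an avoidable gap in which knowledge of the arm can produce untreated subjects without outcomes in the primary population, and the replacement rule does not mend it. A net excess of about 3 subjects from Arm 2 would take a 5% test to 7.6%, and about 6 would take it to 11.1%. About 6 from Arm 1 would cost roughly 12 points of power (89.2% to 77.5%).

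These are illustrations, not predictions. They assume 280 per arm, all leavers scored as non-responders, net loss in one arm only and no other missing responses. The type I error figures also assume a true difference exactly at the margin, and the power figures assume no true difference. The documents do not support a claim that the trial is biased toward noninferiority, or that the bias is large. They support a cheap change of order that closes the gap whichever arm would lose more.

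**What to change.** In Sections 5.3.1 and 7.1, have the enrollment module release the arm only after administration of the common Visit 1 dose has been recorded. Generating the assignment at that moment has the same effect. The manual back-up randomization mentioned in Section 5.3.1 needs the same order, and the sentence on randomization and first dose in Section 4 should be aligned. Reword the replacement sentence in Section 5.3.4 so that it covers only subjects who leave before the arm is released; they cannot be reacting to an assignment that they do not know.

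Every ITT subject whose arm has been disclosed will then have received the first dose. Dropout after disclosure remains possible, so this reduces arm-related loss but does not abolish it. Dose, visits and sample size are unchanged. The cost is a setting in the existing system, a short protocol edit and one extra data-entry step at Visit 1 before the arm is shown.
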